### **9.3.1 Serious Adverse Events**

Any AE that meets a protocol-defined serious criterion must be submitted immediately (within 24 hours of site awareness) on an SAE form to the DMID Pharmacovigilance Group, at the following address:

DMID Pharmacovigilance Group  
Clinical Research Operations and Management Support (CROMS)  
[name]  
[name]  
SAE Hot Line: [name] (US) or [name] (outside US)  
SAE [contact] (US) or [name] (outside US)  
SAE Email Address: [[contact]](mailto:[contact])

In addition to the SAE form, selected SAE data fields must also be entered into Advantage eClinicalSM. Please see the protocol-specific MOP for details regarding this procedure.

Other supporting documentation of the event may be requested by the DMID Pharmacovigilance Group and should be provided as soon as possible.

The site will send a copy of the SAE report(s) to the ISM (as deemed necessary) when they are provided to the DMID Pharmacovigilance Group. The DMID Medical Monitor and DMID Clinical Project Manager will be notified of the SAE by the DMID Pharmacovigilance Group.

The DMID Medical Monitor will review and assess the SAE for regulatory reporting and potential impact on subject safety and protocol conduct.

At any time after completion of this trial, if the site PI or appropriate sub-investigator becomes aware of an SAE that is suspected to be related to study product, the site PI or appropriate sub-investigator will report the event to the DMID Pharmacovigilance Group.

### **9.3.2 Regulatory Reporting for Studies Conducted Under DMID-Sponsored IND**

Following notification from the site PI or appropriate sub-investigator, DMID, the Investigational New Drug (IND) sponsor, will report any suspected adverse reaction that is both serious and unexpected. DMID will report an AE as a suspected adverse reaction only if there is evidence to suggest a causal relationship between the drug and the AE. DMID will notify the FDA and all investigators (i.e., all participating VTEU site PIs to whom the sponsor is providing drug under its IND(s) or under any PI's IND(s)) in an IND safety report of potential serious risks from clinical trials or any other source, as soon as possible, but in no case later than 15 calendar days after the sponsor determines that the information qualifies for reporting as specified in 21 CFR Part 312.32. DMID will also notify the FDA of any unexpected fatal or life-threatening suspected adverse reaction as soon as possible, but in no case later than 7 calendar days after the sponsor's initial receipt of the information. Relevant follow up information to an IND safety report will be submitted as soon as the information is available. Upon request from the FDA, DMID will submit to the FDA any additional data or information that the agency deems necessary, as soon as possible, but in no case later than 15 calendar days after receiving the request.

All serious events designated as "not related" to study product(s) will be reported to the FDA at least annually in a summary format.

### **9.3.3 Reporting of Pregnancy**

Upon awareness, pregnancies occurring in subjects will be recorded on the Pregnancy Report DCF. All pregnancies reported during the course of this trial will be followed to pregnancy outcome. With the subject's permission, a venous blood sample(s) for serological assays will be collected per protocol though large volume blood samples for cellular immunological assays will be discontinued. Subjects who become pregnant will not be excluded from receiving the seasonal flu vaccine at Day 90, unless there are contraindications. Subjects will be followed for safety as per the protocol.

Pregnant subjects will be contacted at least once every 12-16 weeks during pregnancy, following delivery, and at approximately one month following birth (if live birth) or one to two months following still birth.

Subjects who become pregnant will be approached regarding their interest to enroll in the Sanofi Pregnancy Registry. This Registry program is not a part of this research study. Participation is completely voluntary. If subjects choose to enroll they can contact Sanofi via email at [[contact]](mailto:[contact]) or call Customer Service at [name] option#2 to discuss enrollment in the Pregnancy Registry for Influenza.

## **9.4 Type and Duration of Follow-up of Subjects after Adverse Events**

AEs will be collected, assessed and followed through resolution from the time of first study vaccination through approximately 28 days after the first study vaccination.

SAEs and AESIs (including Protocol Specified AESIs, MAAEs, NOCMCs and PIMMCs) will be collected, assessed and followed from the time of the first study vaccination through resolution even if this extends beyond the trial-reporting period (approximately 12 months after the first study vaccination).

Resolution of an AE/SAE is defined as the return to pretreatment status or stabilization of the condition with the expectation that it will remain chronic.

Follow-up procedures, evaluations and outcomes will be recorded on the appropriate DCF and entered into the eCRF.

## 9.5 Halting Rules

Enrollment will start with 6 sentinel subjects, one each from each study group (groups 1-6). Subjects will be followed through Day 8. If any of the pre-specified events outlined in [Section 9.5.1](#) occur, the study will be halted and reviewed by the DSMB. If no prespecified events occur, randomization and vaccination can proceed. All 6 subjects will then be followed according to protocol.

It is anticipated that both adjuvant formulations (AF03 and Advax-CpG55.2) will be available at the start of study enrollment. However, if the Advax or CpG55.2 components for Advax-CpG55.2 are not available, the study will proceed only with groups 1, 2, 4 and 5 open for enrollment for the remaining subjects (up to 240) in groups 1, 2, 4 and 5. For the sentinel subjects, one subject from groups 1, 2, 4 and 5 will be enrolled and followed through Day 8. If any of the pre-specified halting rules occur, the study will be halted and reviewed by the DSMB. If no pre-specified events occur, randomization will proceed in groups 1, 2, 4 and 5 and enrollment will continue for the remaining subjects in groups 1, 2, 4 and 5.

### 9.5.1 Halting Rules for the Sentinel Subjects

- Any subject experiences ulceration, abscess or necrosis at the injection site.
- Any subject experiences laryngospasm, bronchospasm or anaphylaxis within 24 hours after administration.
- Any subject experiences generalized urticaria (defined as occurring at more than two body parts) within 72 hours after administration of study product.
- Any subject experiences an SAE (except for accident or trauma) after administration of the study product.
- Any subject experiences acute weakness of limbs and/or cranial nerve innervated muscles (description of potential signal of GBS) after administration of study product.
- Any subject that experiences grade 3 AE including lab, local or systemic solicited reactogenicity events (excluding measured grades of erythema and induration alone)

- Two or more subjects experience the same grade 2 (same HLG by MedDRA coding) AE including local or systemic solicited reactogenicity events (excluding measured grades of erythema and induration alone)

### 9.5.2 Halting for Study

Additional enrollment and study interventions/administration of study products in this trial will be halted for DSMB review/recommendation if any of the following are reported after the first study vaccination:

- Any subject experiences ulceration, abscess or necrosis at the injection site that is considered related to study product administration.
- Any subject experience laryngospasm, bronchospasm or anaphylaxis within 24 hours after administration of study product that is considered related to study product.
- Two or more subjects experience generalized urticaria (defined as occurring at more than two body parts) within 72 hours after administration of study product that is considered related to study product.
- Any subject experiences an SAE after administration of study product that is considered related to study product.
- Any subject experiences acute weakness of limbs and/or cranial nerve innervated muscles (description of potential signal of GBS) after administration of study product.
- Any subject develops a PIMMC after administration of study product.
- 10% of subjects (minimum 3 subjects) experience a grade 3 injection site or systemic solicited adverse event (excluding measured grades of erythema and induration alone).
- 10% of subjects (minimum 3 subjects) experience same grade 3 AE (unsolicited and laboratory abnormality), in the same HLG by MedDRA coding, considered related to study product.

Grading scales for solicited injection site and systemic (subjective and quantitative) reactions are included in [Section 9.2.2](#).

Grading scales for clinical safety laboratory AEs are included in [Section 9.2.3](#).

If any of the halting rules are met following any subject receipt of study vaccination, then this trial will not continue with the remaining enrollments or study vaccinations without a review by and recommendation from the DSMB to proceed.

DMID retains the authority to suspend additional enrollment and study interventions/administration of study products during this trial, as applicable.

The DMID Medical Monitor is empowered to stop enrollment and study vaccinations if AEs that meet the halting criteria are reported.

## **9.6 Safety Oversight**

### **9.6.1 Independent Safety Monitor (ISM)**

An ISM is a physician with relevant expertise whose primary responsibility is to provide to DMID an independent safety assessment in a timely fashion. This is a voluntary position that does not receive payment. The ISM must meet the requirements of the NIAID Conflict of Interest (COI) policy.

**For this clinical trial an ISM is not required.** However, at each participating VTEU site, **upon DMID Medical Monitor request**, the site PI will identify a physician with relevant expertise, to act as a Secondary Medical Assessor (SMA). The SMA will examine a subject and/or medical records and provide to DMID a medical assessment (or second medical opinion) of the safety event in question. The site PI or appropriate sub-investigator will send to the DMID Medical Monitor, a summary of the event and include the site PI or appropriate sub-investigator and SMA assessments.

Note: In the case that DMID has requested this type of evaluation multiple times, DMID may request the participating VTEU site(s) identify an ISM to assist DMID with safety oversight. Data and Safety Monitoring Board (DSMB)

### **9.6.2 Data and Safety Monitoring Board (DSMB)**

Safety oversight will be conducted by a DSMB that is an independent group of experts that monitors subject safety and advises DMID. The DSMB members will be separate and independent of study personnel participating in this trial and should not have scientific, financial

or other COI related to this trial. The DSMB will consist of members with appropriate expertise to contribute to the interpretation of the data from this trial.

The DSMB will operate under the rules of a DMID-approved charter that will be written at the organizational meeting of the DSMB. At this time, each data element that the DSMB needs to assess will be clearly defined. Procedures for DSMB reviews/meetings will be defined in the charter. The DSMB will review applicable data to include, but not limited to, study progress and subject, clinical, safety, reactogenicity, and immunogenicity data. Reports may include enrollment and demographic information, medical history, concomitant medications, physical assessments, clinical laboratory values, dosing compliance, solicited and unsolicited AE, SAEs, AESIs (including Protocol Specified AESIs, MAAEs, NOCMCs and PIMMCs) and HAI and Neut antibody assay results. The DSMB will review SAEs on a regular basis and ad hoc during this trial. The DMID Medical Monitor and the ISM (as deemed necessary) will be responsible for reviewing SAEs in real time.

The DSMB will review the data when the 8-day reactogenicity and clinical safety laboratory data following the first study vaccination is available for 50% of study subjects. Enrollment will not be paused for this review.

The DSMB will conduct the following reviews:

- An Organizational Meeting that occurs prior to subject enrollment
- Scheduled Data Review Meeting when 50% of the subjects reach Day 8 post first injection and all clinical safety laboratory data following the first study vaccination are available.
- Scheduled Data Review Meeting when an expedited report containing safety and immunogenicity analyses for HAI, NAI and Neut antibody assays unblinded by group has been created by the SDCC after the interim clinical database is cleaned, monitored and locked and all HAI, NAI, and Neut data for Day 1 and Day 29 and safety data through Day 57 after the first study vaccination have been received. If other immunological analyses are available, these data may be reviewed at this meeting.
- Ad hoc when a halting rule is met, or DMID/DSMB chair may convene an ad hoc meeting if there are immediate concerns regarding observations during the course of this trial. The DMID Medical Monitor is empowered to stop enrollment and study vaccinations if AEs that meet the halting criteria are reported.
- Final review meeting may be conducted: 6 to 8 months after clinical database lock to review the cumulative unblinded safety and immunogenicity data for this trial. If a final meeting is held, the data may be provided in a standard summary format, or provided as

the CSR. The DSMB may be asked to provide recommendations in response to questions posed by DMID.

Additional data may be requested by the DSMB, and interim statistical reports may be generated as deemed necessary and appropriate by DMID. The DSMB may receive data in aggregate and presented by treatment arm. The DSMB may also be provided with expected and observed rates of the expected AEs in an unblinded fashion and may request the treatment assignment be unblinded for an individual subject if required for safety assessment. The DSMB will review grouped and unblinded data in the closed session only. As an outcome of each review/meeting, the DSMB will make a recommendation as to the advisability of proceeding with study vaccinations, as applicable, and to continue, modify or terminate this trial.

## **10 CLINICAL MONITORING**

### **10.1 Site Monitoring Plan**

Site monitoring is conducted to ensure that the human subjects' protections, study and laboratory procedures, study interventions/administration of study products, and data collection processes are of high quality and meet sponsor and ICH E6 GCP guidelines and applicable federal regulations, and that this trial is conducted in accordance with the protocol, protocol-specific MOP and applicable sponsor SOPs. DMID, the sponsoring agency, or its designee will conduct site-monitoring visits as detailed in the clinical monitoring plan. DMID-designated clinical monitors will verify that this trial is conducted, and data are generated, documented (recorded), and reported in compliance with the protocol, ICH E6 GCP guidelines and applicable regulatory requirements. Clinical monitoring reports will be submitted to DMID.

Site visits will be made at standard intervals as defined by DMID and may be made more frequently as directed by DMID. Monitoring visits will include, but are not limited to, review of regulatory files, accountability records, eCRFs, ICFs, medical and laboratory reports, and protocol and GCP compliance. Site monitors will have access to each participating VTEU site, study personnel and all study documentation according to the DMID-approved site monitoring plan. Study monitors will meet with site PIs to discuss any problems and actions to be taken and document visit findings and discussions.

## **11 STATISTICAL CONSIDERATIONS**

### **11.1 Introduction**

The goal of this clinical study is to assess, in healthy adults ages 18-45, the safety, reactogenicity and immunogenicity of either the 2018/2019 seasonal Fluzone or Flublok QIV manufactured by Sanofi Pasteur administered intramuscularly given without adjuvant or with one of two adjuvants, AF03 or Advax-CpG55.2. These study arms are included to allow evaluation of the potential of each of the two adjuvants to enhance the immune response to either the 2018/2019 seasonal Fluzone QIV or the 2018/2019 seasonal Flublok QIV.

### **11.2 Study Hypotheses**

This Phase I study is not designed to test a formal null hypothesis. Rather, it is intended to obtain sufficient data to obtain meaningful estimates of the immune response induced by either the 2018/2019 seasonal Fluzone or Flublok QIV administered without adjuvant or with AF03 or Advax-CpG55.2 adjuvants, and to uncover any safety issues that occur at a sufficiently high rate that they might be observed in a study of this size. The sample size facilitates formal testing of selected hypotheses as discussed in [Section 11.4.3](#), along with the probability of observing safety outcomes and the precision of immunogenicity outcomes.

### **11.3 Study Outcome Measures**

Please refer to Study Outcome Measures outlined in [Table 1](#).

### **11.4 Sample Size Considerations**

Please refer to Study Design outlined in [Section 4](#).

#### **11.4.1 Study Population**

The study population for this clinical trial includes males and non-pregnant females, 18-45 years of age, who are in good health and meet all eligibility criteria. The subjects will be recruited from the general population at each of the participating VTEU sites that have substantial experience conducting large influenza vaccine studies.

### 11.4.2 Subject Enrollment and Follow-up

Based on the accrual rates observed in similar studies, it seems reasonable to expect that the participating VTEUs will be able to enroll this trial in a timely fashion. In a previous DMID trial (DMID 15-0064, NCT02624219), 4 VTEUs recruited 275 healthy subjects, 19 to 64 years of age, in 20 weeks. In this trial, approximately 3% of subjects, 19 to 64 years of age, were excluded from the per protocol (PP) analysis for the Day 22 primary immunogenicity outcome either because they were lost-to-follow-up or because they had a protocol deviation requiring their exclusion from the PP analysis. The rate of per protocol exclusions for the Day 29 visit in this protocol is expected to follow a similar trend.

A total of 40 subjects will be enrolled and randomized in each group. Assuming up to 3% drop out by Day 29, it is expected that at least 38 subjects per group will be available for the primary immunogenicity analysis. If Advax-CpG55.2 is not available, the study will proceed only with groups 1, 2, 4 and 5 open for enrollment for the remaining subjects (up to 240 or 60 per group) in groups 1, 2, 4 and 5. In this case, assuming the same dropout rate of 3%, it is expected that at least 58 subjects per group will be available for the primary immunogenicity analysis.

Follow-up will consist of 2 segments. The first encompasses the core data for this trial and will consist of results for all study visits through approximately 28 days after study vaccination. The second segment consists of a 6-month immunogenicity assessment and follow-up safety assessments through approximately 12 months after study vaccination.

### 11.4.3 Sample Size

This study is planned to enroll 40 subjects per group. If Advax-CpG55.2 is not available, the study will proceed only with groups 1, 2, 4 and 5 open for enrollment for the remaining subjects (up to 240 or 60 per group) in groups 1, 2, 4 and 5. This study is not designed to test a formal null hypothesis. Rather, it is intended to obtain sufficient data to obtain meaningful estimates of the immune response and to uncover any safety issues that occur at a sufficiently high rate that they might be observed in a study of this size. For the purposes of summarizing we will assume a type one error rate,  $\alpha = 0.05$ , and will not adjust for multiple comparisons. The following tables illustrate the precision and power for select estimates and comparisons of interest. [Table 10](#) indicates the probability of observing one or more safety events, such as solicited injection site or systemic reactogenicity events or an unsolicited non-serious AE of a particular type for sentinel subjects (N=4 or 6), for a single adjuvanted/ unadjuvanted treatment arm/stratum (N = 40 or 60), for all subjects receiving the same seasonal QIV (N= 120), for all subjects in the trial (N=240).

**Table 10: Probability (%) to Detect Safety Events**

Event Frequency	N = 4	N = 6	N = 40	N = 60	N = 120	N = 240
≥10% Very Common	34	46	98	>99	>99	>99
≥1% Common	3	5	33	45	70	91
≥0.1% Uncommon	<1	<1	3	5	11	21
≥0.01% Rare	<1	<1	<1	<1	1	2

Binomial confidence intervals (CI) are widest (have the least precision) when the response rate is 50%. [Table 11](#) is presented to indicate the worst-case scenario for precision of observed exact (Clopper-Pearson) binomial confidence intervals.

**Table 11: Precision of Binomial Confidence Intervals**

N	95% CI
4	6-94
6	11-89
40	33 -67
60	36-64
120	40-60
240	43-57

For each of the primary immunogenicity objectives, a power analysis is provided below for testing the following hypotheses with the planned sample size, where  $p_c$  = proportion of responders in comparator arm; where  $p_e$  = proportion of responders in experimental arm.

Test for difference in proportion responders:

$H_0: p_c - p_e = 0$  – No difference in proportion responders

$H_1: p_c - p_e \neq 0$  – difference in response rates

[Table 12](#) illustrates the minimum detectable differences in the proportion of subjects responding (e.g., attaining seroconversion or a titer  $\geq 1:40$ ) between two adjuvanted treatment arms using a two-sided Likelihood Ratio Test and  $\alpha = 0.05$ . It is assumed that approximately 3% of the

subjects (N=2) in each treatment arm will be excluded from the per protocol analysis of primary immunogenicity endpoints leaving N=38 subjects per treatment arm. If Advax-CpG55.2 is unavailable, approximately 3% of the subjects (N=2) in each treatment arm will be excluded from the per protocol analysis of primary immunogenicity endpoints leaving N=58 subjects per treatment arm. Seroconversion rates of 40% to 90% are considered.

**Table 12: Minimum Detectable Difference in Proportion Responders with 80% Power**

Assumed Proportion of subjects with titer $\geq 40$ in comparator arm ( $p_c$ )	Minimum detectable difference in response rate ( $p_c - p_e$ ), N=38 per group	Minimum detectable difference in response rate ( $p_c - p_e$ ), N=58 per group
0.40	0.32	0.26
0.50	0.30	0.25
0.60	0.28	0.23
0.70	0.24	0.20
0.80	0.18	0.16
0.90	0.10	0.10

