5. SAMPLE SIZE CONSIDERATIONS

This study is planned to enroll a total of 40 subjects in each group. This study is not designed to test a formal null hypothesis. Rather, it is intended to obtain sufficient data to obtain meaningful estimates of the immune response and to uncover any safety issues that occur at a sufficiently high rate that they might be observed in a study of this size. As such, the type one error rate, $\alpha = 0.05$, is not adjusted for multiple comparisons. While this study is not designed to test any specific null hypothesis, the following tables illustrate the precision and power that is available for select estimates and comparisons of interest.

[Table 3](#) indicates the probability of observing one or more safety events, such as solicited injection site or systemic reactogenicity events or an unsolicited non-serious AE of a particular type for sentinel subjects (N=4 or 6), for a single adjuvanted/ unadjuvanted study arm/stratum (N = 40 or 60), for all subjects receiving the same seasonal QIV (N= 120), for all subjects in the trial (N=240).

Binomial confidence intervals (CI) are widest (have the least precision) when the response rate is 50%.

[Table 4](#) is presented to indicate the worst-case scenario for precision of observed exact (Clopper-Pearson) binomial confidence intervals.

[Table 5](#) illustrates the minimum detectable differences in the proportion of subjects responding (e.g., attaining seroconversion or a titer $\geq 1:40$) between two adjuvanted study arms using a two-sided Likelihood Ratio Test and $\alpha = 0.05$.

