8.1. Primary Immunogenicity Analysis

The primary immunogenicity endpoints HAI, Neut and NAI seroconversion, percentage of subjects with titer $\geq 1:40$ for HAI and Neut only, GMTs, ratios of GMTs between adjuvanted and unadjuvanted groups, and GMFRs against the 2018/2019 QIV strains 28 days after study vaccination (Day 29) will be summarized as described above. The primary analysis population will be mITT, with results from the PP population providing a comparison of the sensitivity of immunogenicity results to subject adherence to protocol-defined conditions.

Summaries of primary immunogenicity endpoints are presented for the 2018/2019 QIV strains in [Table 21](#), [Table 22](#), [Table 23](#), [Table 24](#), [Table 25](#), [Table 26](#), [Table 27](#), and [Table 28](#) for HAI, [Table 29](#), [Table 30](#), [Table 31](#), [Table 32](#), [Table 33](#), [Table 34](#), [Table 35](#), and [Table 36](#) for Neut, and [Table 53](#), [Table 54](#), [Table 55](#), [Table 56](#), [Table 57](#), [Table 58](#), [Table 59](#), and [Table 60](#) for NAI.

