9.7.1 Sample Size**Table 3: Probability (%) to Detect Safety Events**

Event Frequency	N = 4	N = 6	N = 40	N = 60	N = 120	N = 240
≥10% Very Common	34	46	98	>99	>99	>99
≥1% Common	3	5	33	45	70	91
≥0.1% Uncommon	<1	<1	3	5	11	21
≥0.01% Rare	<1	<1	<1	<1	1	2

Table 4: Precision of Binomial Confidence Intervals

N	95% CI
4	6-94
6	11-89
40	33 -67
60	36-64
120	40-60
240	43-57

Table 5: Minimum Detectable Difference in Proportion Responders with 80% Power

Assumed Proportion of subjects with titer ≥ 40 in comparator arm (p_c)	Minimum detectable difference in response rate ($p_c - p_e$), N=38 per group	Minimum detectable difference in response rate ($p_c - p_e$), N=58 per group
0.40	0.32	0.26
0.50	0.30	0.25
0.60	0.28	0.23
0.70	0.24	0.20
0.80	0.18	0.16
0.90	0.10	0.10

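### The 80%-power table prints an unattainable entry (comparator 0.90, N=38), and its difference columns carry the wrong sign

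*Protocol*

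**What the plan says.** Protocol 11.4.3 defines p_c as the responder proportion in the comparator arm and p_e as that in the experimental arm. It gives detectable differences "between two adjuvanted treatment arms using a two-sided Likelihood Ratio Test" at alpha 0.05, with no multiplicity adjustment. The numbers per arm are 38 for the six-arm design (40 enrolled less 2 exclusions) and 58 for the four-arm fallback. Table 12, "Minimum Detectable Difference in Proportion Responders with 80% Power", covers comparator rates from 0.40 to 0.90, and both difference columns are headed p_c − p_e. In the 0.90 row both columns read 0.10. The SAP carries the same figures as "Table 5: Minimum Detectable Difference in Proportion Responders with 80% Power" and describes the comparison in section 5 as "between two adjuvanted study arms using a two-sided Likelihood Ratio Test".

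Protocol 11.2 says the study tests no formal null hypothesis. It then adds, pointing to 11.4.3: "The sample size facilitates formal testing of selected hypotheses". The purpose of the arms is given in protocol 11.1: "These study arms are included to allow evaluation of the potential of each of the two adjuvants to enhance the immune response".

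**The concern.** Two features of the table look wrong on reading. In every other row the difference is smaller at N=58 than at N=38, but the 0.90 row prints 0.10 for both. That value is also exactly the ceiling, 1 − 0.90, which suggests the N=38 entry is the limit of the scale and not a solution for 80% power. In addition, a positive p_c − p_e means the experimental arm does worse, yet the trial asks whether adjuvants improve the response.

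The N=38 column describes the preferred design. High comparator rates are where an adjuvant has least room to show a gain, and titer ≥1:40 is one of the responses the table is meant to cover. A reader could take a null comparison against a 90% comparator as having been adequately powered. Protocol 11.5 allows the Day 29 results to be used in planning later trials, so that misreading could be carried forward.

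**Working it through.** **Inputs** (protocol 11.4.3 and Table 12): two-sided likelihood ratio test (LRT), alpha 0.05 (critical chi-square 3.841), power 80%, equal arms of n = 38 or 58, comparator rates 0.40 to 0.90.

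**Asymptotic power.** With f(p) = p ln p + (1−p) ln(1−p), f(1) = 0 and p̄ = (p_c + p_e)/2:

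- noncentrality λ = 2n[f(p_c) + f(p_e) − 2f(p̄)]
- power = Φ(√λ − 1.96) + Φ(−√λ − 1.96)

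**Step 1: reproduce the table.** Solving for p_e − p_c at 80% power, with p_e above p_c:

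| p_c | N=38 solved | N=38 printed | N=58 solved | N=58 printed |
|---|---|---|---|---|
| 0.40 | 0.316 | 0.32 | 0.258 | 0.26 |
| 0.50 | 0.3025 | 0.30 | 0.250 | 0.25 |
| 0.60 | 0.277 | 0.28 | 0.232 | 0.23 |
| 0.70 | 0.239 | 0.24 | 0.203 | 0.20 |
| 0.80 | 0.1845 | 0.18 | 0.162 | 0.16 |
| 0.90 | no solution | 0.10 | 0.099 | 0.10 |

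Eleven of the twelve cells agree to two decimals, so this is very probably the method used.

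**Step 2: the failing cell, asymptotic.** f(0.90) = −0.3251 and f(0.95) = −0.1985, so the bracket is −0.3251 + 0 + 0.3970 = 0.0719.

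- n = 38: λ = 76 × 0.0719 = 5.47, √λ = 2.338, power = Φ(0.378) = 64.7%
- n = 40: λ = 5.76, power 67.0%
- n = 55: power 80.3%, the first n to reach 80%
- n = 58: λ = 8.35, power 82.4%

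**Step 3: the failing cell, exact.** If all 38 experimental subjects respond, the LRT statistic is 2.83 with two comparator non-responders and 4.28 with three. The test therefore rejects at three or more. For a binomial with n = 38 and probability 0.10, P(X ≥ 3) = 74.6%. The same cutoff has a true type I error of 9.1% at a common response rate of 0.95, so part of the gain over 64.7% comes from an inflated error rate. Exact power is 77.7% at n = 40, first passes 80% at n = 42 (80.5%), and is 93.8% at n = 58.

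**Step 4: how far off.** At N=38, the highest comparator rate from which 100% response is detectable with 80% power is about 0.86 (asymptotic) or 0.89 (exact).

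**Step 5: the sign.** Taking p_e = p_c − d with the printed d, asymptotic power down the rows from 0.40 to 0.90 is:

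- N=38: 92%, 79%, 69%, 57%, 41%, 23%
- N=58: 89%, 80%, 70%, 60%, 49%, 33%

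The p_c = 0.50 row is symmetric. From 0.60 upward the printed values do not give 80% power as decreases.

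**The case against.** - **Nothing hangs on the cell.** This is true. The tables are illustrative, and the SAP reports responder proportions by arm with Clopper-Pearson intervals and plans no LRT on them. That limits the consequence but does not make the entry right, and protocol 11.2 does point to this section for formal testing.
- **Exact power misses by only about five points.** This is fair: the asymptotic approximation is weak when one proportion is 1.00 and the comparator arm expects 3.8 non-responders. Both figures should be given. The exact figure comes with a 9.1% type I error, and neither figure reaches 80%.
- **Another method may have been used.** An arcsine approximation gives 80.1% for this cell. It is not the named test, however, and it yields 0.31, 0.27 and 0.23 at N=38 where the table prints 0.32, 0.28 and 0.24.
- **The real number per arm may exceed 38.** SAP 8.1 states: "The primary analysis population will be mITT", so arms could be nearer the planned 40, and stratified permuted blocks can leave an arm slightly above or below that. At 40, power is 67.0% or 77.7%, still short; the exact calculation needs 42 and the asymptotic 55.
- **Other cells also fall short as printed.** At the rounded 0.18 (p_c 0.80, N=38), asymptotic power is 76.5%. That is rounding of 0.1845, not a separate error, so the other cells are correct to rounding.
- **The sign is only notation.** Many readers would infer gains from the context. Power depends on direction away from 0.50, though, so the label should match the numbers.

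**Conclusion.** The concern holds. With the named test at N=38, no increase over a 90% comparator rate is detectable with 80% power. The maximum is about 65% (asymptotic) or 75% (exact), and 80% would need 55 or 42 per arm respectively. The error is confined to that one cell; the other eleven stand to rounding when read as gains. The header sign is a labelling error, not a miscalculation. Describing the comparison as between two adjuvanted arms fits poorly with the stated purpose but changes no number.

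The conclusion assumes equal arms, the two-sided LRT at unadjusted alpha 0.05, and the numbers per arm in the protocol. The practical effect is small because no planned decision uses the table.

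**What to change.** In protocol Table 12 and SAP Table 5:

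1. Replace the 0.90, N=38 entry with: not attainable (maximum power about 65% asymptotic LRT, about 75% exact).
2. Relabel both difference columns p_e − p_c.
3. Optionally, in protocol 11.4.3 and SAP section 5, describe the comparison as an adjuvanted arm against its matching unadjuvanted arm.

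The cost is one cell, two headers and, if wanted, one phrase in each document. Enrollment, design and analyses are unaffected.
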